11.6.2.2. Handling of Missing Data for Statistical Analysis

Element	Reporting Detail
Critical Errors	
 • If any of the critical error assessment elements (sub-questions) have a missing response then, for the purposes of the analysis of the percentage of subjects making at least one critical error, the subject will be defined as having one or more critical errors. All summarised data and listed data at the individual question level will show that response to be missing. Note that if a subject already has a critical error in another question then the missing response will not impact their error status.
Overall Errors	
 • If any of the error assessment elements have a missing response then, for the purposes of the analysis of the percentage of subjects making at least one error, the subject will be defined as having one or more errors. All summarised data and listed data at the individual question level will show that response to be missing. Note that if a subject already has an error in another question then the missing response will not impact their error status.

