9.1.1. Assessment of Errors in Use of Device

Within each sub-study, subjects will be randomised for the order of treatment. One treatment will require subjects to demonstrate use of a single inhaler (ELLIPTA), while the other treatment will require the subject to demonstrate use of 2 inhalers (DISKUS-HandiHaler in Sub Study 1 or Turbuhaler-HandiHaler in Sub Study 2).

Subjects will be provided with the relevant section of the PIL, explaining correct use, for each inhaler they are to be tested on. The critical and over all errors per inhaler and how these have been defined are included in Appendix 2.

The errors listed will be in aligned with the correct use information from the respective PILs, in a checklist for each inhaler and these will be provided to HCPs for scoring errors during the study conduct. The checklists will be provided in the Study Reference Manual.

Figure 2 depicts the process flow for assessing inhaler use errors and further details are provided, for each treatment, in Section 9.1.1.1 and Section 9.1.1.2.

Figure 2 Assessment of errors in use for each DPI tested**9.1.1.1. Assessment of ELLIPTA error in use**

Subject will be asked to read the patient instruction leaflet for ELLIPTA and then demonstrate ELLIPTA use. Any errors (critical or non-critical) made by the subject while using the ELLIPTA will be recorded by the HCP on the checklist provided. If the subject makes no errors, this will also be recorded by the HCP, and there will be no further assessments. If the subject makes any error in the use of the ELLIPTA, the HCP will provide instruction in the correct use of the ELLIPTA to the subject. The subject will then demonstrate ELLIPTA use again. If the subject makes no errors, this will be recorded by the HCP and there will be no further assessments. If the subject again makes errors in the use of the ELLIPTA any errors will be recorded by the HCP. The HCP will again provide instruction in the correct use for the final time, following which the subject will then demonstrate ELLIPTA use one final time. Any errors made during this demonstration will be recorded. There will be no further assessments. In total, the HCP can provide instruction in the use of the inhaler up to two times.

9.1.1.2. Assessment of DISKUS-HandiHaler in Sub Study 1, or Turbuhaler-HandiHaler in Sub Study 2, for error in use

Subjects will be provided with 2 inhalers and 2 PILs dependent on which sub study they are included in.

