Subjects should be tested on each DPI provided consecutively, they will be tested in the following order for each sub study.

- Sub Study 1: DISKUS followed by HandiHaler

- Sub Study 2: Turbuhaler followed by HandiHaler

Subjects will be asked to read the patient instruction leaflet for the first DPI (DISKUS or Turbuhaler) and then demonstrate first DPI use. Any errors (critical or non-critical) made by the subject while using the first DPI will be recorded by the HCP on the checklists provided. If the subject makes no errors, this will also be recorded by the HCP and there will be no further assessment for this first DPI. If the subject makes any error in the use of the first DPI, the HCP will provide instruction in the correct use of the inhaler to the subject. The subject will then demonstrate inhaler use again. If the subject makes no errors, this will also be recorded by the HCP and there will be no further assessments for this DPI. If the subject again makes errors in the use of the DPI, the HCP will record the errors and provide instruction in correct use for the final time. The subject will then demonstrate use of first DPI for one final time. Any errors or correct use after this demonstration will be recorded, and there will be no further assessments for this DPI. In total, the HCP can provide instruction in the use of the first DPI up to two times.

This assessment will then be repeated with HandiHaler.

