10.2. Sample Size Determination

The sample size calculation for each sub-study is based on the primary endpoint, the percentage of subjects making at least one critical error in each device combination (Ellipta or DISKUS - HandiHaler or Turbuhaler - HandiHaler) after reading the patient information leaflet(s).

Based on the results from studies 201301 and 201330, a range of critical error rates (at least one critical error using each device after reading the patient information leaflet) for each of the treatment options (ELLIPTA, DISKUS - HandiHaler and Turbuhaler - HandiHaler) were explored.

Using 10000 simulations, a total of 72 subjects in each sub-study will provide at least 90% power to show a statistically significant difference between the critical error rate of each of the paired treatment options (Sub-study 1: Treatment option 1 vs. Treatment Option 2; Sub-study 2: Treatment option 1 vs. Treatment Option 3) assuming the following true critical error rates.

Treatment Option 1:	Treatment Option 2:	Treatment Option 3:
ELLIPTA Critical Error Rate	DISKUS - HandiHaler Critical Error rate	Turbuhaler - HandiHaler Critical Error rate
11%	>=37%	>=37%
10%	>=35%	>=35%
9%	>=34%	>=34%
8%	>=32%	>=32%
7%	>=31%	>=31%
6%	>=29%	>=29%

The error rates for the combined treatment options were based on the studies 201301 and 201330 and a conservative assumption that the critical error rate for the combined treatment was the same as the critical error rate for a single device i.e. subjects who made errors made them on both devices.

Conditional logistic regression and a two-sided 5% significance level were used as the analysis method in the simulations. No withdrawal is expected in this single visit study however up to 80 subjects may be randomised to each sub-study to ensure we have 72 evaluable subjects in each sub-study.

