12.2. Appendix 2: Inhaler Specific Errors for the inhalers used in the study

There are no universally agreed checklists that define critical errors and over all errors for specific inhalers. The checklist and critical errors, for use in this study have been developed by GSK for each inhaler based upon:

- A review of the patient information leaflet for each inhaler and the steps defined therein for correct use
- The available literature which is exhaustive for a number of the commonly used inhalers
- Review of these errors with a group of external inhaler experts

The critical errors checklist are, therefore, as robust as possible. Furthermore, GSK has used selected sites with trained assessors to ensure as much consistency as possible in the valuation of errors in study subjects.

Checklist of instructions for correct use will be based on the steps listed in the patient information leaflets/package insert for each device. Some of the steps outlined in the patient information leaflets/package inserts require several actions to be identified and checked by the HCP.

Critical Errors are identified in **bold text** in the list below. A critical error is defined as an error that is most likely to result in no or significantly reduced medication being inhaled.

These errors will be captured in a checklist provided for HCP assessment of DPI use.

DISKUS/ACCUHALER
Failed to open cover
Lever is not pushed back
Shook the device after dose preparation
No exhalation before an inhalation
Exhaled directly into mouthpiece
No seal by the lips round the mouthpiece during the inhalation
Inhalation manoeuvre: 
 - steady - deep
Did not hold breath
Did not close the device (Note: this is an error but one which does not affect the medication that is inhaled)
Any other comments: [free text box]

ELLIPTA
Failed to open cover
Shook the device after dose preparation
No exhalation before an inhalation
Exhaled directly into mouthpiece
No seal by the lips round the mouthpiece during the inhalation
Inhalation manoeuvre: 
 - long - steady - deep
Blocked air inlet during inhalation manoeuvre
Did not hold breath
Did not close the device (Note: this is an error but one which does not affect the medication that is inhaled)
Any other comments: [free text box]

TURBUHALER
Failed to remove cap
Did not hold device upright ($\pm 45\%$ OK) during dose preparation

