Base not twisted fully backwards and forwards, no click heard
Device tipped downwards after dose preparation
Shook the device after dose preparation
No exhalation before an inhalation
Exhaled directly into mouthpiece
No seal by the lips round the mouthpiece during the inhalation
Inhalation manoeuvre: 
 - forceful - deep 
Note to HCP: it is important that the inhalation is forceful and deep from the start for this inhaler

Blocked air inlet during inhalation manoeuvre
Did not hold breath
Did not close the device (Note: this is an error but one which does not affect the medication that is inhaled)
Any other comments: [free text box]

HANDIHALER
Failed to remove capsule
Failed to insert capsule into the chamber
Did not completely close device capsule chamber (heard click when satisfactory)
Did not pierce the capsule (HCP should check capsule was pierced)
Shook the device after dose preparation
No exhalation before an inhalation
Exhaled directly into mouthpiece
No seal by the lips round the mouthpiece during the inhalation
Inhalation manoeuvre: 
- slow- deep
Capsule did not rattle
Blocked air inlet during inhalation manoeuvre
Did not hold breath
Did not check inside the capsule chamber if powder was left / did not make a second inhalation
Any other comments: [free text box]

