Where required by applicable regulatory requirements, an investigator signatory will be identified for the approval of the clinical study report. The investigator will be provided

reasonable access to statistical tables, figures, and relevant reports and will have the opportunity to review the complete study results at a GSK site or other mutually-agreeable location.

GSK will also provide the investigator with the full summary of the study results. The investigator is encouraged to share the summary results with the study subjects, as appropriate.

The procedures and timing for public disclosure of the results summary and for development of a manuscript for publication will be in accordance with GSK Policy.

Data Quality Assurance

- All participant data relating to the study will be recorded on printed or electronic CRF unless transmitted to the sponsor or designee electronically (eg, laboratory data). The investigator is responsible for verifying that data entries are accurate and correct by physically or electronically signing the CRF.
- The investigator must maintain accurate documentation (source data) that supports the information entered in the CRF.
- The investigator must permit study-related monitoring, audits, IRB/IEC review, and regulatory agency inspections and provide direct access to source data documents.
- The sponsor or designee is responsible for the data management of this study including quality checking of the data.
- Study monitors will perform ongoing source data verification to confirm that data entered into the CRF by authorized site personnel are accurate, complete, and verifiable from source documents; that the safety and rights of participants are being protected; and that the study is being conducted in accordance with the currently approved protocol and any other study agreements, ICH GCP, and all applicable regulatory requirements.
- Records and documents, including signed ICF, pertaining to the conduct of this study must be retained by the investigator for 25 years after study completion unless local regulations or institutional policies require a longer retention period. No records may be destroyed during the retention period without the written approval of the sponsor. No records may be transferred to another location or party without written notification to the sponsor.

Source Documents

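### Scoring a blank checklist element as an error acts through 22 or 25 printed rows on the two-inhaler option against 9 on ELLIPTA, and no planned run gives the after-PIL overall-error result without that rule

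*SAP*

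**What the plan says.** **Rule.** SAP 11.6.2.2 treats a subject with any blank error element as having made an error: "at least one error, the subject will be defined as having one or more errors". A blank changes nothing if another error is already recorded. The same section adds: "All summarised data and listed data at the individual question level will show that response to be missing". A parallel rule covers critical errors.

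**Checklists.** Protocol Appendix 2 lists the errors for each inhaler and says: "These errors will be captured in a checklist provided for HCP assessment of DPI use". Protocol 9.1.1 places the operative forms elsewhere: "The checklists will be provided in the Study Reference Manual". The comparator option is two inhalers tested one after the other, each with its own checklist.

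**Analysis.** SAP 8.1.2.2 analyses overall errors after the PIL by the method of SAP 7.1.2: conditional logistic regression with treatment option and period, stratified by subject. The model is fitted only if there are enough data. The one sensitivity analysis is a Cochran-Mantel-Haenszel (CMH) test on err_ord (SAP 11.5.3), reported in Table 2.10.

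**The concern.** Counting a blank as an error looks conservative. It would be even-handed if both options had the same number of elements. They do not, so a common blank rate per row forces more errors onto the two-inhaler option, which is the direction in which the trial hopes to find a difference.

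The CMH run changes the test, but err_ord is built from the same had-error or had-no-error status and nothing exempts it from the rule. The country covariate does not alter the status either, and the exclusion of subjects with only one period (SAP 11.6.2) is a different provision. Question-level displays would show that blanks exist. They would not show how the odds ratio or p-value moves without the rule, and example shell EFF_T01 has no row for missing responses.

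**Working it through.** **1. The plan's own figures.** The documents give no row total, blank rate or expected overall-error rate. The power statement in Protocol 10.2 (at least 90% with 72 subjects) concerns critical errors and is not used here. For the record, with independent responses a likelihood-ratio test of the planned model gives 96–97% in all six scenarios. A Wald test with period that counts separated fits as not significant gives 59–81%.

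**2. Rows** (Protocol Appendix 2, free-text row left out).
- ELLIPTA 9, DISKUS 9, Turbuhaler 12, HandiHaler 13. The thirteenth HandiHaler row is "Did not check inside the capsule chamber if powder was left / did not make a second inhalation".
- Sub-study 1: 9 + 13 = 22 against 9. Sub-study 2: 12 + 13 = 25 against 9.
- With manoeuvre sub-items scored separately (three for ELLIPTA, two for each other inhaler): 11 against 10 + 14 = 24 or 13 + 14 = 27.

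**3. Assumptions.** Let m be the blank rate per row (independent, same for all inhalers) and t the true overall-error rate, set equal on both options so that any difference is false. Protocol 10.2 plans comparator critical-error rates of at least 29–37%, "assuming the following true critical error rates". Overall errors include critical ones, so t = 35–75% is taken as the main range.

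**4. Formulas.**
- Chance of at least one blank over k rows: 1 − (1 − m)^k.
- Scored error rate: 1 − (1 − t)(1 − m)^k.
- False risk difference: (1 − t)[(1 − m)^9 − (1 − m)^k], with k = 22 or 25. Example with t = 35%, m = 1%, k = 25: 0.65 × (0.9135 − 0.7778) = 8.8 points.
- Test: in each sequence take the log ratio of the two kinds of discordant pair; the treatment effect is the mean of the two. Two-sided 5% Wald test, 36 subjects per sequence, independent true errors, separated fits counted as not significant, 200,000 simulated trials per cell.

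**5. Results.**

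| Blanks per row | At least one blank: 9 / 22 / 25 rows | False difference, t = 35% | False difference, t = 75% | False claims for ELLIPTA, t = 35–75% |
|---|---|---|---|---|
| none | 0 | 0 | 0 | 2.1–2.4% |
| 0.1% | 0.9 / 2.2 / 2.5% | 0.8–1.0 points | 0.3–0.4 points | 2.4–3.0% |
| 0.5% | 4.4 / 10.4 / 11.8% | 3.9–4.8 points | 1.5–1.8 points | 3.4–7.7% |
| 1% | 8.6 / 19.8 / 22.2% | 7.3–8.8 points | 2.8–3.4 points | 4.8–17.4% |

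The nominal rate in ELLIPTA's favour is 2.5%. The upper ends belong to t = 35% with 25 rows, the lower ends to t = 75%.

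**6. Where it fades.**
- At t = 85% the Wald test gives 1.9–2.0% at 0.5% blanks and 2.3–2.6% at 1%. These do not meaningfully exceed 2.5%, although they are above that test's own 1.5% with no blanks.
- If blanks come as whole checklists, with probability m per inhaler, the contrast is one inhaler against two: at m = 1%, 1.0% against 1 − 0.99² = 2.0%. False claims are then 2.2–2.7%.

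**The case against.** **The size rests on unsupplied inputs.** This stands. At 0.1% blanks the effect is negligible. At 1% independent blanks, about 20–22% of subjects would have an incomplete two-inhaler record after the PIL. That is hard to square with live scoring at one supervised visit, trained assessors, and the commitment that "Study monitors will perform ongoing source data verification". Responses recorded as not applicable or not evaluable are not treated as missing (SAP 11.6.2). The 75% ceiling on true rates is also a choice; the documents support only a floor for the comparator.

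**The row counts come from the protocol, not from the operative forms.** This stands too, since the Study Reference Manual was not supplied. Scoring sub-items separately leaves the direction unchanged.

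**The plan already shows missing responses.** It does at question level, and with about 72 subjects per sub-study the forced errors could probably be counted from the listings. That still gives no re-estimated odds ratio. That the CMH run uses the imputed status is inferred from SAP 11.5.3, not stated, but nothing suggests otherwise.

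**Readings that go too far.**
- A reader might infer that the primary endpoint is biased in the same way. The same kind of rule applies to it, but the bold marking of critical rows is lost in the text available. Shell EFF_T01 marks them for ELLIPTA only, so the critical rows cannot be compared.
- A reader might carry the 22 or 25 against 9 over to the assessments after HCP instruction. Fewer rows apply there: after correct use of the first inhaler, "there will be no further assessment for this first DPI".
- A reader might take 17% as the expected false-claim rate. It is the top of an assumed range.

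**Conclusion.** The point holds for the after-PIL overall-error endpoint. One prespecified rule acts through unequal numbers of rows, favours ELLIPTA when true error rates and per-row blank rates are equal, and is not removed in any planned run. How much this matters cannot be settled from the documents: under the stated assumptions it runs from nothing noticeable at 0.1% blanks per row to a clear excess of false claims at 1% with true rates near 35%. It shrinks as true error rates rise and as blanks cluster by checklist. The documents do not show an effect on the primary endpoint, nor that blanks will be common. This is a robustness gap on a secondary endpoint, worth closing because it is cheap to close before database freeze.

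**What to change.** Keep the main rule and add to SAP 11.6.2.2:

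> The Section 7.1.2 conditional logistic regression for the after-PIL overall-error endpoint, and for the after-PIL critical-error endpoint because the same rule applies, will be repeated with error status determined from observed elements only (a missing element is not counted as an error). If any inhaler of a treatment option has a wholly blank checklist, that option is treated as not assessed and the subject is excluded from this run.

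Report the odds ratio, 95% CI and p-value beside the main result, in Tables 2.09 and 2.11 or in an extended Table 2.10, whose shell EFF_T07 now carries only a CMH p-value. Add the number of subjects per treatment option whose error status was set only by a missing element. The critical-error run is included because the rule is shared, not because an effect has been shown.

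**Cost.** One extra run and one count. The run assumes that blanks do not hide errors and may look slightly less favourable to ELLIPTA than the main rule. If each true error sits in one row and is hidden with probability m, its false-claim rate is 2.4–2.7%, or at most 3.4% if blanks hide errors on ELLIPTA only. At assumed true rates of 35% against 60%, its power is 84.5–85.2%, against 85.2% with no blanks and 86–93% under the planned rule. Restricting to complete checklists is an alternative that removes the tilt if blanks are random, but it would leave about 61–62 of 72 subjects at 0.5% blanks and 51–53 at 1%.

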11.7. Appendix 7: Multicenter Studies**11.7.1. Methods for Handling Centres**

Element	Reporting Detail
Centres	
• Central randomisation was used for this study. Data from all participating centres will be pooled prior to analysis.

11.8. Appendix 8: Examination of Covariates, Subgroups & Other Strata

11.8.1. Handling of Covariates

- The following is a list of covariates that may be used in descriptive summaries and statistical analyses. Whilst inhaler sequence will be used throughout, the inclusion of country in the model relies on sufficient data being collected in each country to allow the model to remain statistically valid. If the model is valid the data the analysis will be performed.
- Country will be included as a covariate as part of a sensitivity analysis if enough subjects from each country are recruited, within each of the possible outcomes (critical error/no critical error) by device and randomised sequence, to allow the statistical model to converge without errors.

Category	Covariates and / or Subgroups
Inhaler Sequence	The study inhaler use sequence (ELLIPTA/Other or Other/ELLIPTA) which include information on the treatment and period it was received in will be adjusted for in the statistical analysis. Other refers to either DISKUS + HandiHaler or Turbuhaler + HandiHaler.
Country	This study will be carried out in two countries (the United Kingdom and the Netherlands), summary tables will be provided by country and it may be included in statistical sensitivity analysis if enough subjects from each country are recruited, within each of the possible outcomes (critical error/no critical error) by device and randomised sequence, to allow the statistical model to converge without errors.

11.9. Appendix 9: Model Checking and Diagnostics for Statistical Analyses

Model	Diagnostic Checks
Logistic Regression	Residual vs Fitted plots will be generated to help assess the constant variance assumption. Deviance and Pearson goodness of fit statistics from the model will be examined to help assess the null hypothesis that the model is an adequate fit to the data.
Cochran-Mantel-Haenszel	Homogeneity across groups will be assessed using the Breslow-Day test. SAS Code: <pre>proc freq data = pref_data (where = (pref_ord ne 0)) ; tables country * seq * pref_ord / cmh ; run;</pre>

All model checking statistics will be assessed but not formally reported in a table, listing or figure.

